6.2.3 Follow-up period and trial completion

For all patients, termination of trial medication and trial completion must be recorded on the corresponding eCRF.

For patients completing the safety FU period, the EOS visit is scheduled at 16 weeks after the last dose of study drug. For more details please follow [Flow Charts](#).

6.2.3.1 Early treatment discontinuation

Patient who discontinue treatment prior to the planned EOT visit have to be invited for an early EOT visit as soon as possible. These patients should be registered as withdrawn from treatment in IRT and return to the site for the End of Study (EOS) visit 16 weeks after last study drug intake.

6.2.3.2 Trial completion

Patients who finish the treatment period will return to the site for the End of Study (EOS) visit 16 weeks after the EOT visit. Completion is defined as a patient having reached the EOS visit.

6.2.3.3 Further treatment after the end of the trial

At the end of the trial, patients will be treated for their CD at the discretion of the investigator, according to local CD guidelines.

7. STATISTICAL METHODS AND DETERMINATION OF SAMPLE SIZE

This trial is designed as a single arm, open-label trial in patients with fistulising Crohn's disease who have completed the planned treatment period in the parent induction trial.

There is no confirmatory statistical testing planned during the analysis of this extension trial, only descriptive analyses are intended.

7.1 NULL AND ALTERNATIVE HYPOTHESES

Given the single arm and open-label nature of this trial, all statistical assessments will be performed in a descriptive manner only. No hypothesis testing is intended to be performed.

7.2 PLANNED ANALYSES

7.2.1 General considerations

There will be only one patient population in this trial for analyses – the Treated Set (TS). The TS includes all patients who received at least one dose of study drug. It will be the main analysis set for presentation of both safety and efficacy.

Further analysis sets will be defined in the TSAP if necessary.

Important violations of the protocol will include violations of the key inclusion and exclusion criteria, concomitant use of restricted medications, and any other violations of the protocol deemed important by the study team. All decisions concerning important protocol violations will be made prior to final database lock for this extension trial.

Standard statistical parameters (number of non-missing values, mean, standard deviation (SD), median, quartiles, minimum, and maximum) or frequency tables (including patient frequencies and percentages) will be calculated where appropriate.

A Clinical Trial Report will be prepared once the final database lock for this extension trial has been performed.

7.2.2 Primary endpoint analyses

Refer to [Section 2.1.2](#) for the description of the primary endpoint. The primary analyses will be descriptive in nature. All treated patients will be included in the primary analyses. No hypothesis testing is planned.

Adverse events will be coded using the Medical Dictionary for Drug Regulatory Activities (MedDRA). Standard BI summary tables and listings will be produced. All adverse events with an onset between start of treatment of this trial and end of the residual effect period

(REP), a period of 16 weeks after the last dose of trial medication, will be assigned to the on-treatment period for evaluation.

Adverse events that start before first drug intake and deteriorate under treatment will also be considered as 'treatment-emergent'. For all patients who, due to a fistula relapse received the intensified treatment with spesolimab, safety assessments including adverse events, laboratories, vital signs, etc., which occurred subsequent to such intake will be excluded from presentations according to the planned treatment; these data will, however, be included in summaries where all data after any use of spesolimab are displayed.

Exposure-adjusted adverse event incidence rates will be calculated using the following approach:

The incidence rate (per 100 patient years) of a selected adverse event (also known as the incidence density rate or person-time incidence rate) is defined as the number of patients experiencing the adverse event during the time at risk divided by the total time of patients at risk to contribute an event to the analysis multiplied by 100, where:

$$\text{Time at risk (in subject years)} = ((\text{date of onset of AE} - \text{study drug start date}) + 1) / 365.25$$

The study drug start date refers to the start date of this trial. If, for a patient, no treatment emergent adverse event occurred, then the time at risk will be censored at the minimum of: date of death; drug stop date + 112 days; start date of CD inflammatory flare or fistula relapse treatment with spesolimab; last contact date; or, date of database snapshot if an interim analysis was performed.

For each AE, the incidence rate will therefore be calculated as:

$$\text{Incidence rate} = 100 * \text{number of patients with TEAE} / \text{Total TEAE-specific time at risk.}$$

Exact 95% confidence intervals around the observed AE incidence rate will also be provided.

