6. GENERAL ANALYSIS DEFINITIONS

6.1 TREATMENT(S)

For basic study information on treatments to be administered, assignment of treatment groups, and selection of doses, refer to CTP Section 4.

Patients who experience a fistula relapse during the maintenance treatment (as defined in CTP Table 2.1: 1) will be administered a single intravenous dose of spesolimab 1200 mg followed by an intensified subcutaneous maintenance dosing schedule with 600 mg q4w.

The following study periods are defined:

Table 6.1: 1 Flow chart of analysis periods which apply to all patients.

Analysis period	On-/off- treatmen t	Start (included)	End (included)
Screening period (Approx 1-2wks)	Off- treatment	Earliest of (Date of informed consent, first screening procedure)	Date/time of injection of first s.c. maintenance study drug minus 1 minute.
Overall maintenance period ¹ (Approx 336 wks)	On- treatment	Date/time of first s.c. maintenance study drug.	Date of last administered spesolimab (irrespective of formulation) + 112 days at 11:59pm.
Follow-up period ²	Off- treatment	Date of last study drug administration (irrespective of formulation) + 113 days at 12:00 AM.	Latest of: i) Date of EOS visit (Week 352 visit); ii) last contact date on End of Study page at 11:59 p m.

Dates are defined individually per patient. If more than one date is associated with a specific visit, measurements associated with a specific date are assigned to a study analysis phase according to the rules specified in the table. An analysis phase will not extend beyond the start date of the following phase.

The on-treatment period is defined as the overall maintenance period (including REP).

For all analysis periods, assessments done on the same day as the first maintenance treatment dose will be assigned to the appropriate analysis phase based on the assessment of date/time. If time is not collected for an assessment, then assignment will be to the previous analysis phase, e.g., to the screening phase.

Treatment Labels

Treatments will be labelled as follows:

"Overall Speso"

¹ The overall maintenance treatment period applies to all patients taking at least one dose of maintenance treatment regardless of flare occurrence. This period will be considered to understand long-term efficacy and safety of spesolimab.

² The follow-up period only exists if the trial completion date is after the date of end of last injection/infusion plus REP.

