7.7 EXTENT OF EXPOSURE

A table of total treatment exposure [mg] across the overall maintenance period will be summarized for the SAF for spesolimab s.c. and spesolimab i.v., respectively. For the time at risk, and for the total duration of exposure(weeks), data will also be tabulated as a frequency table with categorized treatment duration, (i.e., >0 to 48 weeks, >48 to 96 weeks, >96 to 144 weeks) for the SAF for 'Overall Speso' only.

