7.8.1 Adverse events

AEs will be coded with the most recent version of MedDRA.

The analysis of AEs will be descriptive in nature. All analyses of AEs will be based on the number of patients with AEs and not on the number of AEs. System organ classes (if applicable) will be sorted according to the standard sort order specified by the EMA. Preferred terms (if applicable) will be sorted by total frequency (within system organ class).

For further details on summarization of AE data, please refer to "Analysis and Presentation of Adverse Event Data from Clinical Trials" (4) [KM Asset BI-KMED-BDS-HTG-0041] and "Handling of missing and incomplete AE dates" (3) [KM Asset BI-KMED-BDS-HTG-0035].

The analysis of AEs will be based on the concept of treatment emergent AEs. This means that all AEs will be assigned to either the screening period, the applicable on-treatment period, or the off-treatment period (i.e. follow-up) as defined in Section 6.1. Since only the start date of an AE is collected (without start time), any AE which occurs on the same day as the first maintenance treatment will be assigned to the respective on-treatment period.

Refer to CTP Section 7.2.2 for a description of the calculation of exposure-adjusted adverse event incidence rates (per the primary endpoint).

The AE summaries described below will be produced for the following treatment periods:

• The overall maintenance period [based on the SAF]

An overall summary of AEs will be presented. This overall summary will include the class of AESIs. Refer to CTP Section 5.2.6.1.4 for a description of what is considered as an AESI.

The investigator identified AESI will be captured from the eCRF and reported in the "Investigator reported AESI" table. In addition, user defined adverse event categories (UDAEC) identified through specific search criteria will be reported separately; the UDAEC applicable to this trial are stored centrally and will be referenced for this presentation.

Adverse Events classified as 'other significant' will be reported using an adaptation of the ICH E3 (6) and will include those non-serious and non-significant AEs which were reported with 'action taken = drug withdrawn' or 'action taken = reduced'.

Table 7.8.1: 1 Project MEDDRA search criteria for User Defined Adverse Events Categories (UDAEC)

User-defined AE category			
Label	Description		
Infections ALL	Combined search strategy based on the individual UDAECs for infections described below		

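### SAP reports AE rates for 'Overall Speso' but keeps a time-at-risk rule that stops event-free patients at relapse treatment

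*Protocol*

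**What the plan says.** Protocol Section 7.2.2 plans two kinds of safety presentation. Presentations by planned treatment leave out data collected after intensified spesolimab for fistula relapse. For the other kind, "these data will, however, be included in summaries where all data after any use of spesolimab are displayed".

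The same section gives a single rule for the rate. It is the "number of patients experiencing the adverse event during the time at risk divided by the total time of patients at risk", times 100. A patient with the event contributes time from first dose in this trial to AE onset. A patient without it is censored at the earliest of several dates: death, drug stop plus 112 days, the "start date of CD inflammatory flare or fistula relapse treatment with spesolimab; last contact date", or a database snapshot.

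The SAP defines one treatment label, 'Overall Speso', and one on-treatment period. Table 6.1:1 ends that period at "Date of last administered spesolimab (irrespective of formulation) + 112 days at 11:59pm". Its first footnote adds: "The overall maintenance treatment period applies to all patients taking at least one dose of maintenance treatment regardless of flare occurrence". SAP 7.8.1 produces AE summaries for this period only and requires exposure-adjusted rates by system organ class (SOC) and preferred term (PT). For the formula it says: "Refer to CTP Section 7.2.2 for a description of the calculation of exposure-adjusted adverse event incidence rates (per the primary endpoint". SAP 5.1 states when time at risk begins but not when it ends, and also points to Protocol 7.2.2. SAP 7.7 adds, for 'Overall Speso' only: "For the time at risk, and for the total duration of exposure(weeks), data will also be tabulated as a frequency table".

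**The concern.** The relapse-treatment stop belongs to the planned-treatment presentation, which the SAP no longer produces. Carried into an 'Overall Speso' rate, it can be applied in two ways.

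- **Reading 1 (events after re-induction count).** SAP 6.1 and 7.8.1 class these AEs as on-treatment, and the protocol formula runs to onset with no cap for patients who have the event. Re-induced patients without the event still stop at relapse treatment. Numerator and denominator then cover different periods, and the error is upward or zero.
- **Reading 2 (events after re-induction are dropped).** The protocol's phrase limiting events to the time at risk can be taken this way. Numerator and denominator then match, but the rate omits all events and exposure after the 1200 mg infusion and on 600 mg every 4 weeks, while labelled as all spesolimab.

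Two programmers could follow the same text and report different rates. Safety is the primary endpoint, so the SOC and PT rates matter even in a descriptive trial. SAE, AESI and user-defined category rates are affected only if they use the same formula; the SAP promises separate tables for them without naming rates.

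**Working it through.** The documents state no event rate, relapse count or relapse timing, so there is no figure of theirs to reproduce. From the documents: up to 20 patients (Protocol 7.5), a residual effect period of 16 weeks = 112 days, and exposure categories up to 144 weeks (SAP 7.7). Everything else below is assumed. PY means patient-years; the censoring sentence is read separately for each AE because the protocol's denominator is specific to the TEAE.

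**Expected size under reading 1.** Constant hazard L, the same before and after re-induction; follow-up F; a fraction p re-induced at time r and followed to Fr. Per patient:

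- Events = (1−p)(1−e^(−L·F)) + p(1−e^(−L·Fr))
- Matched time = events / L
- Reading 1 time = (1−p)(1−e^(−L·F))/L + p[(1−e^(−L·Fr)(1+L·Fr))/L + r·e^(−L·Fr)]

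Example: L = 0.10 per year, F = Fr = 48 weeks = 0.920 y, r = 0.5 y, p = 0.5. Events = 0.0879. Matched time = 0.879 y, or 17.58 PY for 20 patients. Reading 1 time = 0.687 y, or 13.75 PY. The rate becomes 12.79 instead of 10.00 per 100 PY.

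| Re-induced at 6 months | 48 weeks | 2 years |
|---|---|---|
| 0% | 0% | 0% |
| 10% | +5% | +3% to +7% |
| 25% | +12% | +8% to +20% |
| 50% | +28% | +21% to +51% |

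In the 2-year column the low end stops follow-up 28 weeks after re-induction and the high end follows everyone for the full 2 years. With 0–50% re-induced at 3–12 months and 48–144 weeks of follow-up, the error runs from 0% to +74% at 5–10 per 100 PY, to +40% at 50 and to +16% at 200. The +74% needs half the patients re-induced at 3 months and all followed for 144 weeks.

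**Same data, three rules** (exact Poisson 95% intervals).

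*48 weeks:* 5 of 20 re-induced at week 26; AE in one patient not re-induced (week 24) and one re-induced (week 36).

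- Matched: 18×48 + 24 + 36 = 924 weeks = 17.71 PY
- Reading 1: 14×48 + 24 + 4×26 + 36 = 836 weeks = 16.02 PY
- Reading 2: 14×48 + 24 + 5×26 = 826 weeks = 15.83 PY

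*2 years:* 10 of 20 re-induced at 0.5 y; AE in two not re-induced (1 y) and two re-induced (1.25 y).

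- Matched: 16×2 + 2×1 + 2×1.25 = 36.5 PY
- Reading 1: 8×2 + 2×1 + 8×0.5 + 2×1.25 = 24.5 PY
- Reading 2: 8×2 + 2×1 + 10×0.5 = 23.0 PY

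| Rate per 100 PY | 48 weeks | 2 years |
|---|---|---|
| Matched | 2/17.71 = 11.3 (1.4–40.8) | 4/36.5 = 11.0 (3.0–28.1) |
| Reading 1 | 2/16.02 = 12.5 (1.5–45.1) | 4/24.5 = 16.3 (4.4–41.8) |
| Reading 2 | 1/15.83 = 6.3 (0.2–35.2) | 2/23.0 = 8.7 (1.1–31.4) |

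**AE with no events**, 5 of 20 re-induced at 6 months. Only the upper limit, 3.689/PY, moves:

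- 48 weeks: 3.689/16.30 = 22.63 instead of 3.689/18.40 = 20.05 per 100 PY
- 2 years: 3.689/32.5 = 11.35 instead of 3.689/40.0 = 9.22 per 100 PY

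**Any TEAE (the primary rate).** Disease worsening is itself recorded as an AE (Protocol 5.2.6.1.1), and relapse is confirmed before the infusion (Flow Chart 2B). Most re-induced patients should therefore already have a TEAE; if all do, the effect is zero. If 19 of 20 have one at a mean of 0.5 y and the other is re-induced at 0.5 y:

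- 48 weeks: 19/(9.5 + 0.5) = 190.0 against 19/(9.5 + 0.92) = 182.3 per 100 PY, +4%
- 2 years: 190.0 against 19/(9.5 + 2) = 165.2 per 100 PY, +15%

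With a mean of 0.25 y the figures are +8% and +29%.

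**The case against.** The best counter-argument is that Protocol 7.2.2 already confines the numerator to events within the time at risk. Read as a whole it then gives reading 2, which is internally consistent, and only a label is at issue. This does not settle the matter. The formula runs time at risk to AE onset for patients with the event and caps only those without, so the phrase does not clearly exclude later events, and SAP 6.1 with 7.8.1 counts them as on-treatment. If it did exclude them, the rate would still not be an overall spesolimab rate.

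Some points do stand:

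- SAP 7.8.1 says "For further details on summarization of AE data, please refer to" an internal standard that is not available here and may resolve the question. Parts of the SAP are also missing from the public copy.
- The sizes are entirely assumed, including equal hazard before and after re-induction. Patients without benefit after re-induction are taken off treatment, so the full-follow-up figures are upper bounds.
- The intervals in the examples overlap widely, no decision rule uses the rates, and crude frequencies and listings are unaffected.
- Stopping both events and time at relapse treatment, with a matching label, would also remove the inconsistency.

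**Conclusion.** The concern holds. As the available text stands, no reading of the rate rule gives what the 'Overall Speso' label promises. Under reading 1, a SOC or PT rate with at least one event is too high whenever a re-induced patient lacks that AE and has later follow-up. Under reading 2, on-treatment events and exposure are left out. Rare terms are affected most in relative size and the any-TEAE primary rate least, although with at most 20 patients a single event-free re-induced patient can still shift the latter. If nobody was re-induced there is no effect. That the SAP and protocol texts do not fit together is clear; how far the reported rates move depends on relapse numbers the documents do not give. It should be corrected, but it does not threaten any decision built into the trial.

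**What to change.** In SAP 5.1 and 7.8.1, state that for 'Overall Speso' rates a patient without the given AE is censored at the earliest of death, last spesolimab plus 112 days, last contact, or data snapshot, with no stop at relapse treatment. Apply the same rule to the time-at-risk table in SAP 7.7. If a planned-treatment rate is also shown, stop both the event count and the time at risk at the start of relapse treatment and label the rate accordingly. List the change in SAP Section 4.

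The protocol's censoring term also names inflammatory-flare treatment with spesolimab, whereas Protocol 3.1 has patients with a luminal flare alone continue the same maintenance dose. The two passages should be reconciled at the same time.

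The cost is one SAP sentence and one derivation line, with no new data.

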7.2.3 Secondary endpoint analyses

Refer to [Section 2.1.3](#) and [Table 2.1:1](#) for a description of the secondary endpoints. All secondary endpoints will be assessed descriptively. Details will be provided in the TSAP.

7.2.5 Safety analyses

Refer to [Section 7.2.2](#) for a description of the analyses of the primary endpoint, which for the present trial is a safety endpoint.

For the additional safety analyses described below, all treated patients will be included. In general, these additional safety analyses will be descriptive in nature and will be based on BI standards. No hypothesis testing is planned.

Statistical analysis and reporting of adverse events will concentrate on treatment-emergent adverse events, i.e. all adverse events occurring between start of treatment in this trial and the end of the REP. Refer to [Section 7.2.2](#) for the complete description of a treatment-emergent adverse event.

Frequency, severity, and causal relationship of adverse events will be tabulated by system organ class and preferred term after coding according to the current version of the Medical Dictionary for Drug Regulatory Activities (MedDRA) at database lock.

Laboratory data will be analysed both quantitatively as well as qualitatively. The latter will be done via comparison of laboratory data to their reference ranges. Values outside the reference range as well as values defined as clinically relevant will be summarised.

Laboratory data will be analysed descriptively with regard to distribution parameters as well as with regard to frequency and percentage of patients with abnormal values or clinically relevant abnormal values.

Vital signs, physical examinations, or other safety-relevant data observed at screening, baseline, during the course of the trial and at the end-of-trial evaluation will be assessed with regard to possible changes compared to findings before start of treatment.

7.2.7 Interim Analyses

In order to ensure the patient's safety during the trial, an external DMC, independent of the trial and project teams, will be set-up to review all available safety data as well as selected efficacy data at regular intervals following first-patient-in. A DMC SAP which describes the analyses required for assessment by the DMC will be produced and finalized prior to the first patient included into the trial. Further details will be provided in a DMC charter.

As the primary aim of this study is to collect long-term safety and efficacy data on the use of spesolimab in this population, multiple interim analyses will be done over the duration of this trial to support, for example, regulatory interactions, CTA and MAA/BLA submissions, but also to provide important safety and efficacy information to the sponsor to guide further development of the compound, and to the investigators via IB updates and publications.

Since patients will be enrolled into this study over a time period of several years and in line with the exploratory nature and open label design of the study, such analyses will be performed on demand and are not feasible to be pre-defined.

A CTR describing all data collected within this trial will be produced after the last patient in the trial has completed the final follow-up visit.

7.3 HANDLING OF MISSING DATA

Every effort will be made to collect complete data at all visits. However, missing data will still occur and approaches to handle this are proposed below.

For the safety data, including the primary endpoint, no missing data imputations are planned.

For the efficacy outcomes derived from [REDACTED], no missing data imputations are planned to be performed.

If a patient experiences an inflammatory flare or fistula relapse during the maintenance period prior to observing the efficacy outcome at a specific visit, then all data subsequent to the intake of such rescue medication will be set to missing. Additional summaries of all data observed, including data gathered following rescue medication intake, will also be provided. Further details with regard to what constitutes a rescue intake with potential impact on the efficacy data will be described in the TSAP.

For other efficacy endpoints, rules for handling of missing data will be specified in the TSAP if necessary.

